4.3.4 Investigational Medicinal Product Accountability

All IMPs required for completion of this study will be provided by the Sponsor. The study site will acknowledge receipt of IMPs supplied by the Sponsor, using the IxRS to confirm the shipment condition and content. Any damaged shipments will be replaced.

IMPs will either be disposed of at the study site according to the study site's institutional standard operating procedure or be returned to the Sponsor with the appropriate documentation. The site's method of destroying Sponsor-supplied IMPs must be agreed to by the Sponsor. The site must obtain written authorization from the Sponsor before any Sponsor-supplied IMP is destroyed, and IMP destruction must be documented on the appropriate form.

Accurate records of all IMPs received at, dispensed from, returned to, and disposed of by the study site should be recorded on the Drug Inventory Log.

4.3.5 Continued Access to Gantenerumab

The Sponsor will offer continued access to Roche IMP gantenerumab free of charge to eligible participants in accordance with the Roche Global Policy on Continued Access to Investigational Medicinal Product, as outlined below.

A participant will be eligible to receive Roche IMP gantenerumab after completing the study if all of the following conditions are met:

- The participant has a life-threatening or severe medical condition and requires continued Roche IMP treatment for his or her well-being.
- There are no appropriate alternative treatments available to the participant.
- The participant and his or her doctor comply with and satisfy any legal or regulatory requirements that apply to them.

A participant will not be eligible to receive Roche IMP gantenerumab after completing the study if any of the following conditions are met:

- The Roche IMP is commercially marketed in the participant's country and is reasonably accessible to the participant (e.g., is covered by the participant's insurance or wouldn't otherwise create a financial hardship for the participant).
- The Sponsor has discontinued development of the IMP or data suggest that the IMP is not effective for AD.
- The Sponsor has reasonable safety concerns regarding the IMP as treatment for AD
- Provision of the Roche IMP is not permitted under the laws and regulations of the participant's country.

The Roche Global Policy on Continued Access to Investigational Medicinal Product is available at the following website:

http://www.roche.com/policy_continued_access_to_investigational_medicines.pdf

4.4 CONCOMITANT THERAPY

Concomitant therapy consists of any medication (e.g., prescription drugs, over-the-counter drugs, vaccines, herbal or homeopathic remedies, nutritional supplements) used by a participant in addition to protocol-mandated treatment from 3 months prior to first administration of study drug in Study WN42171 to the OLE final follow-up visit. All such medications (including name, dose, administration schedule, start and end dates) used by the patient during Study WN42171 should be reported to the investigator and recorded on the Concomitant Medications eCRF.

4.4.1 Permitted Therapy

Participants are eligible for study participation whether or not they are receiving approved medication for AD (i.e., AChEls, memantine, and/or medical food supplements, where approved) with the exception of GV-971. Participants who have received GV-971, are currently receiving GV-971 or who are planning to receive GV-971 during the study are not eligible. Information about background AD medication (e.g., drug name, dose, and start and stop dates, reason for interruption or modification) should be captured on the eCRF.

Adding a new medication or changing the dose of a medication during the study should occur only for the treatment of an adverse event or in case of AD progression. Whenever possible, a medication listed below should be used if appropriate.

The following medications are permitted. Doses are expected to remain stable after baseline:

- Anticonvulsant medications
- Selective serotonin reuptake inhibitors for the treatment of depressive symptoms

- Over-the-counter and/or herbal medications, food additives, or any other agent or supplement intended to improve cognition or reduce cognitive decline
- Medications used to treat a mood or anxiety disorder given as maintenance treatment (with the exception of benzodiazepine)
- Use of short-acting (non-extended release) opioid medications for pain
- Use of benzodiazepines, including alprazolam, lorazepam, oxazepam, triazolam, or temazepam, or short-acting hypnotic medication (e.g., zolpidem)
- A dose of benzodiazepine for pre-surgical and pre-imaging sedation at appropriate visits if allowed by the Ethics Committee (EC) or Institutional Review Board (IRB)
- Use of centrally acting antihistamine medications
- Under certain circumstances, initiation of anti-hemostasis medications during the study conduct

Anticoagulation therapy lasting no longer than 3 weeks (e.g., temporary usage during surgery) is permitted. However, for any such use it is recommended to prospectively seek advice from the Medical Monitor, and study drug *should be temporarily interrupted whilst anticoagulation therapy is ongoing*.

Participants who use oral contraceptives, hormone-replacement therapy, or other maintenance therapy should continue their use.

The administration of COVID-19 vaccines, just as with other vaccinations (e.g., influenza) will be considered as a concomitant medication. Based on the available information, no interactions between gantenerumab or PET tracers and the COVID-19 vaccines are expected to occur, and no other safety concerns have been identified that would prohibit the vaccination of participants enrolled in the studies where gantenerumab is being investigated for the treatment of AD. However, the published safety data for COVID-19 vaccines show that overlapping adverse events between medicines such as gantenerumab and the vaccine can occur: the timing and the nature of local injection reactions (occurring within 24 hours) as well as of systemic injection reactions may be similar for both products. To facilitate the correct clinical assessment of any adverse events and to continue correct attribution of adverse events related to study drugs (gantenerumab and PET tracers) or to the vaccination, namely of local and systemic reactions following the injections, the Sponsor recommends to vaccinate study participants at least 24–48 hours after an injection of study drug. Similarly, vaccination in the 48 hours preceding a study drug administration should also preferably be avoided. However, the timing of the study visits and study drug administration should not be unduly postponed because of a vaccination.

4.4.2 Prohibited Therapy

The following medications are prohibited at study start and during the entire period of study participation. Participants who start these medications during the study may be withdrawn from study treatment:

- Any active immunotherapy (vaccine) that is being evaluated to prevent or postpone cognitive decline
- Any passive immunotherapy (immunoglobulin) or other long-acting biologic agent that is under evaluation or approved to prevent or postpone cognitive decline within 1 year of screening, except for gantenerumab
- Any other investigational treatment or any other treatment with an investigational monoclonal antibody within 5 half-lives or 4 months prior to screening, whichever is longer
- Any previous administration of GV-971
- Anti-coagulation medications
 - Anti-platelet treatments (e.g., aspirin, clopidogrel, and dipyridamol) are permitted.
 - Short-term, perioperative use of anticoagulant medications will not result in permanent discontinuation from the study; however, for any such use, it is recommended to prospectively seek advice from the Medical Monitor and *study drug should be temporarily interrupted whilst anticoagulation therapy is ongoing.*

The following medications *should preferably be avoided* in this study *although they* are *not strictly prohibited*:

- Stimulant medications (amphetamine, methylphenidate preparations, or modafinil) throughout the study
- Typical antipsychotic or neuroleptic medication
- Atypical antipsychotic medications
- Chronic use of opiates or opioids (including long-acting opioid medication)
- Chronic use of benzodiazepines, barbiturates, or hypnotics

If possible, use should be limited to intermittent short-term use. Consideration should be made as to whether clinically appropriate to interrupt the medication 2 days or at least 5 half-lives (whichever is longer) prior to any neurocognitive assessment due to their psychoactive effects.

4.5 STUDY ASSESSMENTS

The schedule of activities to be performed during the study is provided in Appendix 1. All activities should be performed and documented for each participant. At applicable sites, certain study assessments may be performed by a mobile nursing (MN) professional at the participant's home or another suitable location, such as a nursing center, to improve access and convenience for participants participating in the study. The Sponsor will select a healthcare company that will be responsible for providing MN services for participating sites (the MN vendor). The MN vendor is responsible for ensuring that all MN professionals are licensed, qualified, and in good standing, as per applicable regulations, and that appropriate background checks have been performed. If the investigator at a participant gives written informed consent to participate in MN visits, the MN network will communicate with the participant and the participant's site. MN visits will be scheduled on specified visit days, to allow for relevant assessments to be performed by the MN professional. The schedule of activities (see Appendix 1) specifies the assessments that may be performed by an MN professional.

4.5.1 Informed Consent Forms and Screening Log

Informed consent should be obtained from participants while they are in the parent study (WN29922 or WN39658) including in the safety follow up, until a day before the first dose in the study WN42171. In special situations, informed consent can be obtained at a later timepoint upon providing an appropriate rationale to the Sponsor. Written informed consent for participation in the study must be obtained before performing any study-related procedures. Informed Consent Forms for enrolled participants and for participants who are not subsequently enrolled will be maintained at the study site.

All screening evaluations must be completed and reviewed to confirm that participants meet all eligibility criteria before enrollment. The investigator will maintain a screening log to record details of all participants screened and to confirm eligibility or record reasons for screening failure, as applicable.

4.5.2 Baseline Definition and Assessments

For participants who completed the double-blind part and did not enter the OLE part of study WN29922 or WN39658: The first dosing visit in this study will be considered as baseline (OLE Day 1), and the final efficacy and safety visit assessment of the parent Study (WN29922 or WN39658) will be considered as baseline assessment if occurring within a specific timeframe.

For participants who completed the double-blind part and the OLE part of study WN29922 or WN39658: the baseline visit will be the OLE Day 1 visit of the parent study (WN29922 or WN39658). This group of participants will roll over to study WN42171 upon the completion of their uptitration. The first visit in this study should take place approximately 2 weeks after the OLE Week 34 visit or the last dose visit in the parent study (WN29922 or WN39658) OLE.

On the day of the first dose of gantenerumab in study WN42171, if results of standard-of-care tests or examinations (coagulation, ECG, serum chemistry, and hematology; complete physical examination) performed within 4 weeks are available, they do not have to be repeated. For C-SSRS, and cognitive scale results, the time interval is 6 months. MRI scan does not need to be repeated if performed within 6 months in the parent study and following the final study drug dose in the parent study. Vital signs, urine pregnancy test for women of childbearing potential, collection of adverse events, and review of concomitant medications have to take place before each dose administration. The MRI can only be used if it was the last prescribed per-protocol MRI in the parent study, including those required for ARIA-E follow up.

4.5.3 Medical History, Baseline Conditions, Concomitant Medication, and Demographic Data

Medical history and demographic data as collected in the parent Study WN29922 or WN39658 will be used in this study and should include clinically significant diseases, surgeries, cancer history (including prior cancer therapies and procedures), reproductive status, smoking history, and use of alcohol and drugs of abuse. Medical history and demographic data will be automatically transferred into the study WN42171 eCRF. In addition, ongoing concomitant medications will automatically be transferred from the parent study (WN29922 or WN39658) to study WN42171. All changes to medications during the study (e.g., prescription drugs, over the counter drugs, vaccines, herbal or homeopathic remedies, nutritional supplements) should be recorded in the eCRF. Changes in medical history will be collected once after completion of the double-blind part in the parent study (WN29922 or WN39658) and before OLE Day 1 either in the parent study or in study WN42171.

Demographic data will include age, sex, and self-reported race/ethnicity.

Because this study is being conducted in multiple geographic regions, it is likely that participants of different ethnic origins will be enrolled in the study. Although there is currently no indication that gantenerumab is metabolized or eliminated differently or that the treatment effect would be different in participants of different ethnic origins, collecting this information is essential to adequately evaluate the results of this study (e.g., possible differences in PK exposure [concentration of the drug in the blood] or treatment effect).

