3.1 DESCRIPTION OF THE STUDY

3.1.1 Overview of Study Design

Study WN42171 is an open-label, multicenter, rollover study to evaluate the safety, tolerability, and efficacy of long-term administration of open-label gantenerumab in participants with AD who completed Study WN29922 or WN39658, either the double–blind or OLE part, as applicable (parent study). The blind to the study treatment allocation during the parent study will be maintained to protect study integrity.

Participants who have completed Study WN29922 or WN39658, either the double-blind or OLE part as applicable, will be eligible to participate in this study. Participants who discontinued early from study treatment during Study WN29922 or WN39658, regardless of the reason, will not be eligible for this study.

Informed consent should be obtained from participants while they are in the parent study (WN29922 or WN39658) including in the safety follow-up, until a day before the first dose in the Study WN42171. In special situations, informed consent can be obtained at a later timepoint upon providing an appropriate rationale to the Sponsor, and it must be obtained before any study procedures in this study are performed.

The first administration of gantenerumab in this study will be as follows:

- For participants who completed the double-blind part and did not enter the OLE part of Study WN29922 or WN39658: The first administration of open-label gantenerumab should take place approximately 2 weeks after the last efficacy and safety visit of the double-blind part of the parent study (WN29922 or WN39658) and will be considered the OLE baseline visit (OLE Day 1).
- For participants who completed the double-blind part and the OLE part of Study WN29922 or WN39658, the first administration of gantenerumab in this study should take place approximately 2 weeks after the OLE Week 34 visit or the final dose visit in the Study WN29922 or WN39658 OLE. Participants who have a gap in their transition between the OLE part of the parent study (WN29922 or WN39658) and this study, for unforeseen reasons, will roll over to this study continuing the schedule of activities as per their last visit in the OLE part of the parent study (WN29922 or WN39658). Discussion with the Sponsor is recommended.

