4.5.9 Columbia–Suicide Severity Rating Scale

The C-SSRS (http://www.cssrs.columbia.edu) is an assessment tool used to assess the lifetime suicidality of a participant (C-SSRS at baseline) as well as any new instances of suicidality (C-SSRS since last visit). The structured interview prompts recollection of suicidal ideation, including the intensity of the ideation, behavior, and attempts with actual or potential lethality. The C-SSRS baseline from the parent study will be used, and the C-SSRS since the last visit will be collected at subsequent visits as indicated in the schedule of activities (see Appendix 1).

The assessment will be completed by a certified C-SSRS rater after he or she interviews the participant and the participant's caregiver during the study visit.

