- ^b Results of standard-of-care tests or examinations (coagulation, ECG, serum chemistry, and hematology; complete physical examination) performed within 4 weeks prior to Day 1 may be used. MRI, C-SSRS, and cognitive scale results may be used if they have been performed *at final efficacy and safety visit of the parent study and* within 6 months prior to OLE Day 1. *MRI must have been performed after the last dose in the parent study*. If a clinical RNA sample or plasma biomarker or CSF and matching serum sample (where applicable) was collected at the final efficacy and safety visit of the parent study, another one does not have to be collected.
- ^c At applicable sites, administration of gantenerumab may be performed by a mobile nursing professional at the participant's home or another suitable location, such as a nursing center, to improve access and convenience for participants participating in the study.
- ^d Visit may be split over 2 consecutive days. All cognitive and functional assessments should be completed first. All safety assessments (e.g., vital signs, blood tests, and ECGs) should be completed on the day of dosing. Whenever possible, cognitive and functional assessments should be performed at the visit timepoints stipulated in the schedule of activities. However, in exceptional circumstances, if the caregiver, the primary rater, or even the participant cannot perform these assessments as per the schedule of activities, they may be performed up to 4 weeks out of window.
- ^e Height will be assessed only at the first dosing visit in Study WN42171.
- ^f Accurate recording of the date and time of study drug administration and PK sampling is critical. A PK sample will be obtained as soon as practicable (e.g., at an unscheduled visit or the next study visit) following a MRI scan showing new occurrence or worsening of ARIA–E or ARIA-H that meets the discontinuation criteria (e.g., during an unscheduled visit).

Gantenerumab—F. Hoffmann-La Roche Ltd 112/Protocol WN42171, Version 4

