### 5.1.1 Definition of Baseline

The first dosing visit in the OLE will be considered as baseline (OLE Day 1). The last available assessment made before or on OLE Day 1 will be considered the baseline assessment if occurring within 12 weeks before or on OLE Day 1 and prior to first dose for standard-of-care examinations or within 6 months for C-SSRS, cognitive scale results and MRI scans. For ADA data, baseline will be the baseline value of the parent studies to ensure that the baseline value is before any dose of the investigational product.

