### 5.3.8 Columbia-Suicide Severity Rating Scale (C-SSRS)

The C-SSRS is a tool used to assess the lifetime suicidality of a participant (C-SSRS at baseline) as well as any new instances of suicidality (C-SSRS since last visit). The structured interview prompts recollection of suicidal ideation, including the intensity of the ideation, behavior, and attempts with actual or potential lethality.

Suicidal ideation, suicidal behavior, and self-injurious behavior without suicidal intent will be summarized by previous treatment group and participation / non-participation in the OLE part of the parent studies. In addition, change from baseline to worst post-baseline assessment in suicidality categories will be summarized by previous treatment group and participation / non-participation in the OLE part of the parent studies.

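### For participants who skipped the parent OLE, waiving the OLE Day 1 C-SSRS lets the Week 24 form carry suicidality from before the first OLE dose into the post-baseline tables

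*Protocol*

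**What the plan says.** Protocol 4.5.9 brings only one C-SSRS form into this study: "The C-SSRS baseline from the parent study will be used, and the C-SSRS since the last visit will be collected at subsequent visits". In Appendix 1 Table 1, which covers participants who did not enter the parent OLE, that form is scheduled at OLE Day 1 and Week 24, with nothing scheduled between (unscheduled visits aside).

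The Day 1 form can be waived. Section 4.5.2 says "For C-SSRS, and cognitive scale results, the time interval is 6 months", and the synopsis, 3.1.1 and SAP 1.2 repeat the 6-month allowance. Table 1 footnote b, attached to the Day 1 cell, reads "MRI, C-SSRS, and cognitive scale results may be used if they have been performed" and adds that the parent result must come from the final efficacy and safety visit. Section 3.1.1 also lets data from the last parent visit stand as first-visit data when the two visits are within 4 weeks. The planned interval is shorter than that: "The first administration of open-label gantenerumab should take place approximately 2 weeks after the last efficacy and safety visit of the double-blind part".

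SAP 5.1.1 takes as baseline the last assessment before or on OLE Day 1, "or within 6 months for C-SSRS, cognitive scale results and MRI scans". SAP 5.3.8 then states "Suicidal ideation, suicidal behavior, and self-injurious behavior without suicidal intent will be summarized by previous treatment group", and also "change from baseline to worst post-baseline assessment in suicidality categories will be summarized by previous treatment group". It has no rule on when an event recorded on a form took place.

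**The concern.** An MMSE score is a value at one point in time, so reusing an older one gives only an older value. A since-last-visit C-SSRS records events over an interval, so skipping it at OLE Day 1 removes the boundary between the time before and after the first OLE dose. An episode in the gap comes too late for the parent form and is first recorded at Week 24, where the SAP treats it as post-baseline.

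The C-SSRS is among the primary safety endpoints and is included in the interim analyses in SAP 5.8.1, the first of which supports a potential filing. A former placebo participant who had never received gantenerumab could be shown as having suicidal ideation or behavior on open-label drug. The sponsor draws this boundary for adverse events: SAP 5.3.3 restricts the summary tables to events starting or worsening from the day of the first OLE dose and lists earlier-onset events separately.

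**Working it through.** The plan gives no figure to reproduce, so the check is date arithmetic.

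**Inputs**
- Gap *g* from the last parent C-SSRS to OLE Day 1: about 2 weeks as planned (Protocol 3.1.1), at most 6 months under the waiver (4.5.2, footnote b). Six months is taken as 183 days, the figure the SAP uses in its PET windows.
- Time from OLE Day 1 to the next scheduled form: 24 weeks = 168 days (Appendix 1 Table 1). Visit windows are ignored.
- Assumption: 'since last visit' means since the last C-SSRS. The documents do not define the starting point. Protocol 4.5.9 pairs a lifetime baseline form with a form for new instances, which suggests continuous coverage.

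**Formula**

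Recall at Week 24 = *g* + 168 days. Pre-dose share = *g* / (*g* + 168).

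| Gap | Recall at Week 24 | Pre-dose share |
|---|---|---|
| 14 days (planned) | 182 days | 14/182 = 7.7% |
| 28 days | 196 days | 28/196 = 14.3% |
| 91 days | 259 days | 91/259 = 35.1% |
| 183 days (limit) | 351 days | 183/351 = 52.1% |

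These are shares of recall time, not of events. With a Day 1 form completed before dosing, the Week 24 recall is 168 days and the pre-dose share is 0%.

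**Who is affected.** For participants who completed the parent OLE, baseline is OLE Day 1 in the parent study, and their waiver (Table 3 footnote e) falls at about Week 36, after the first OLE dose. They are outside this point.

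**How often.** At the planned gap, anyone with a C-SSRS at the final parent visit qualifies, so the waiver is open to most of the group. Longer gaps need a delayed rollover. One route is foreseeable: participants with ARIA-E on the last parent MRI stay in the parent study until it resolves (3.1.1). The documents give no frequency for delays.

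**If the form is read literally.** Dosing visits are every 2 weeks, so a Week 24 form starting from the Week 22 visit covers about 2 weeks. It then includes no pre-dose time but leaves the first 22 of the 24 weeks to no scheduled form.

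**The case against.** The strongest reply is that the waiver is deliberate, appears in both documents, and does little harm. At the planned gap it affects about 8% of the recall time. No hypothesis is tested (SAP 2), and results are split by previous treatment and by parent-OLE participation. For the former active arm, the pre-OLE time was not drug-free. All of this stands. It limits the importance of the point but does not supply the missing boundary.

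A reader might go further in four ways that the documents do not support.

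- *That nothing in the records separates events before and after the first dose.* Adverse events are sought at every contact (Protocol 5.3.1), and medical history changes are collected between the end of the double-blind part and OLE Day 1 (4.5.3). An episode also reported as an adverse event can be placed by its onset date. The remaining gap is narrower: under 5.3.5.14 the Sponsor does not derive adverse events from clinical outcome assessments, and sites are not expected to review those data for them. A response recorded only on the form may therefore stay undated.
- *That the error can only add events.* This holds only if the form looks back to the last C-SSRS. On the literal reading the problem is missed events.
- *That about half of the recall is typically pre-dose.* The 52% is the boundary of the waiver, and reaching it needs a delayed rollover.
- *That every participant is affected.* Those who came through the parent OLE are not.

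**Conclusion.** The point holds for participants who did not enter the parent OLE. Following the plan as written, suicidality from before the first OLE dose can enter a post-baseline primary safety table, and SAP 5.3.8 has no rule to prevent or show it. The pre-dose share of the Week 24 recall is about 8% as planned, 14% at a 4-week gap, and at most 52%.

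This rests on reading 'since last visit' as since the last C-SSRS, a reasonable but unstated assumption. Misattribution matters mainly for former placebo participants and for responses not also reported as dated adverse events. The number of events affected cannot be estimated from the documents. The change is worth making because the form is already scheduled at OLE Day 1. The point does not undermine the safety analysis as a whole.

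**What to change.** For participants who did not enter the parent OLE only:

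1. Remove the C-SSRS from the waiver in Appendix 1 Table 1 footnote b and from the matching sentences in the synopsis, 3.1.1, 4.5.2 and SAP 1.2. Except it from the 4-week carry-over of last-visit data, and word the general scale waiver in 4.5.6 so that it does not reach the C-SSRS for this group. Leave Table 3 footnote e unchanged.
2. Complete the scheduled since-last-visit form at OLE Day 1 before dosing. State in 4.5.9 that its recall starts at the last C-SSRS.
3. In SAP 5.1.1 and 5.3.8, treat the Day 1 form as pre-dose and define baseline as the worse of that form and the last parent form within 6 months. Otherwise the current last-available rule would make the Day 1 form alone the baseline, with a look-back of only about 2 weeks at the planned gap.
4. For participants already enrolled without a Day 1 form, flag Week 24 positives as 'recall period includes pre-OLE time' and show the C-SSRS summary with and without them.

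The cost is one short extra interview at an existing visit, a few sentences in the protocol and SAP, and one table flag.
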